This project aims to be completed within three years. This goal is reasonable given our team's expertise in conducting psychophysiological laboratory research working with drug administration (i.e., alcohol and nicotine), community participants, and stress reactivity. Our lab has the experience and infrastructure to recruit and retain a sample of this size. We recently completed a pilot study for the current application that recruited 115 participants (58 alcoholic and 57 matched controls) over the course of 14 months. This study involved diagnostic interviews and stress-reactivity task over the course of two study visits. The current study will plan to initially consent eighty-five participants with a final sample size goal of seventy-two participants. Based on prior experience we anticipate that 85% of eligible participants will return to complete all study visits. A total of 157 complete visits (85 first, 72 second) will be conducted. If we conservatively expect to average 2 study visits per week to account for no-shows, failed eligibility criteria, and equipment failure we anticipate completing data collection within 1.5-2 years.

Reference Cited

1. Erb, S. *et al.* Alpha-2 adrenergic receptor agonists block stress-induced reinstatement of cocaine seeking. *Neuropsychopharmacology* **23**, 138–50 (2000).
2. Pacák, K. *et al.* Effects of various stressors on in vivo norepinephrine release in the hypothalamic paraventricular nucleus and on the pituitary-adrenocortical axis. *Ann. N. Y. Acad. Sci.* **771**, 115–130 (1995).
6. Pacák, K. *et al.* Effects of single or repeated immobilization on release of norepinephrine and its metabolites in the central nucleus of the amygdala in conscious rats. *Neuroendocrinology* **57**, 626–633 (1993).

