In a parallel line of research we have demonstrated that these tasks have proved effective at differentiating drug deprived, dependent users from non-dependent healthy controls for a variety of drugs including tobacco⁵⁵, marijuana⁵⁶, and alcohol⁵⁷. Cigarette smokers displayed elevated startle response selectively during unpredictable stressors (vs. predictable stressors) after 24-hours of nicotine deprivation compared to non-deprived smokers⁵⁵. Dependent marijuana users show significantly increased startle potentiation during unpredictable stressors after three days of abstinence relative to non-deprived smokers and non-smoker controls⁵⁶. Furthermore, alcoholics in 1-8 weeks early abstinence show larger startle potentiation to unpredictable stressors (vs. predictable stressors) compared to healthy controls in a variant of the NPU task⁵⁷. This demonstrates that these tasks provide an objective non-invasive physiological biomarker of the effects of drug deprivation on affective responses to unpredictable stressors that represents an etiologically relevant cross-drug phenomenon.

We believe these data in humans, in combination with ample evidence from rodent models, supports our use of the NPU task to advance translational research aimed at identifying mechanisms for novel pharmacological treatments of stress induced relapse mechanisms in addiction. We also provide this preliminary evidence to confirm that our laboratory has the necessary expertise to work with clinical samples of drug dependent users, acutely administer drugs safely in the laboratory, and measure psychophysiological response (including startle potentiation) during stressor tasks⁵⁵⁻⁵⁸.

REPURPOSING PRAZOSIN

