The site of the proposed research is the University of Wisconsin-Madison. Prospective participants will be recruited through the greater Madison community via paper fliers and online advertisements. Paper flyers will be posted in a variety of locations throughout the UW campus and community (e.g., laundromats, restaurants, gas stations, etc.). Paper flyers will also be posted at targeted locations to recruit recovering alcoholics including community support groups (e.g., AA meeting locations) and local in- and out-patient treatment facilities for alcoholism (e.g., Gateway Recovery, Tellurian, ARC, Connections Counseling, etc.). Participants over the age of 50 will be excluded to limit potential extraneous variance related to normal aging processes. To decrease the risk of adverse psychological reactions in response to startle probes and electric shock, participants will be excluded if they have a lifetime diagnosis of serious and persistent mental illness (SPMI; e.g. bipolar disorder, schizophrenia, any psychosis).

Thirty-six alcohol dependent participants in early protracted abstinence (at least 1 week but no more than 8 weeks since last alcohol use) will be recruited for the study. Thirty-six non-alcoholic participants will also be recruited to will serve as the comparison group. Participants in the alcoholic and control groups will be matched on selected characteristics including age, sex, education level, daily nicotine use, and Axis I psychopathology. These characteristics will be matched at the group level such that the average and range of both groups will be comparable.

Inclusion Criteria

All participants:

Can read and write in English.
Ages of 18-50 years.

Alcoholic Participants:

The alcoholic participants will have at least one but no more than eight weeks completely free from alcohol consumption.

Control Participants:

The control participants must not meet criteria for any current or lifetime history or substance dependence other than nicotine dependence.

Exclusion Criteria

Exclusion criteria are divided into three broad categories of Medical, Psychiatric/Behavioral, and Medications/Therapies. These criteria are all implemented to protect human subject safety, except where noted with an asterisk (*) denoting scientific/theoretical reasons.

Medical exclusion

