- Self-reported acute or unstable illness precluding a safe and reliable study participation; medical conditions precluding participation will include, for example, unstable angina, history of myocardial infarction, history of congestive heart failure, chronic renal or hepatic failure, pancreatitis, Meniere's disease, benign positional vertigo, narcolepsy.
- A pre-existing hypotension (systolic less than 100) or orthostatic hypotension (systolic drop greater than 20mmHg after two minutes standing or any drop accompanied by dizziness).
- Systolic blood pressure greater than 160
- Tachycardia ≥ 100
- Allergy or previous adverse reaction to prazosin or other alpha 1-NE antagonist.
- Women of childbearing potential (see definition below) must agree to use one of the following forms of birth control until after study completion. Acceptable birth control is defined as the following methods of contraception: abstinence; hormonal contraceptives (e.g. combined oral contraceptives, patch, vaginal ring, injectables, and implants); intrauterine device (IUD) or intrauterine system (IUS); vasectomy of partner and tubal ligation; "single" barrier methods of contraception (e.g. male condom, female condom, cervical cap, diaphragm, contraceptive sponge) with use of spermicide; or "double barrier" method of contraception (e.g. male condom with diaphragm, male condom with cervical cap).
- Women who are breastfeeding will be excluded.
- *Color blindness. [Excluded because colored images identify critical differences between predictable, unpredictable, and no-shock conditions in the NPU stress-reactivity task.]

Psychological/Behavioral exclusion

- Self-reported lifetime diagnosis of serious and persistent mental illness, including schizophrenia, schizoaffective disorder, psychotic disorder NOS, delirium, bipolar Disorder, borderline personality disorder, or any neurocognitive disorder.
- Any current active substance use disorder other than tobacco.
- Control Participants Only: Lifetime history of substance dependence.

Medications/Therapies exclusion

- Current use of prazosin or other alpha1-NE antagonist (e.g., doxazosin, terazosin).
- Previous adequate trial of prazosin for alcohol use disorder or PTSD.
- Sildenafil (Viagra), tadalafil (Cialis), and vardenafil (Levitra) will not be permitted during the study because of increased risk of hypotension in combination with alpha1-NE antagonists.

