- *Stimulants (e.g., d-amphetamine, methylphenidate) or alternative medications with stimulant properties (e.g., ephedra). [Excluded because these medications directly alter CNS noradrenergic neurotransmission.]
- *Beta-blockers (e.g., propranolol), alpha2 agonists (e.g., clonidine, guanfacine), and SNRI anti-depressants (e.g., venlafaxine, duloxetine). [Excluded because these medications directly alter CNS noradrenergic neurotransmission.]

Note: Women of childbearing potential are females who have experienced menarche and do not meet the criteria for women **not** of childbearing potential. Women **not** of childbearing potential are females who are permanently sterile (e.g., hysterectomy, bilateral oophorectomy) or postmenopausal. Postmenopausal is defined as 12 consecutive months with no menses without an alternative medical cause.

Research Design and Methods Overview

Overview of Study Procedures

Seventy-two participants (36 alcoholic & 36 controls) will be recruited to participate in a double-blind, placebo-controlled, mixed-design, cross-over study examining the effects of a NE- α 1 antagonist (prazosin) on the affective response to stressors. ~~Both study visits will take place in the Clinical Research Unit (CRU) inpatient unit at the University of Wisconsin Hospital. A screening visit will take place in the Addiction Research Center at the University of Wisconsin – Madison.~~ At the first study screening visit general laboratory procedures and risks and benefits will be explained to the participants and informed consent will be obtained from all participants. Inclusion/exclusion criteria will be confirmed using interviews conducted by a nurse, graduate level clinician, self-report questionnaires and urine test for pregnancy. ~~Study Nursing~~ staff will collect ~~a medical history~~, current medication, orthostatic vital signs, and urine pregnancy test to confirm eligibility. For both participant groups, research staff will first confirm that the potential participant is free from severe and persistent mental illness. Following this, the more in-depth Substance Use Disorders Module of the SCID-Research Version (SCID-RV⁸⁴) will be administered to confirm the alcoholic participants' status with respect to an Alcohol Dependence diagnosis and no lifetime history of substance dependence for control participants. Participants will complete a shock sensitivity rating as per standard procedures from our laboratory.

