Eligible participants will be scheduled for two study visits that will take place in the Clinical Research Unit (CRU) inpatient unit at the University of Wisconsin Hospital. Modifiable inclusion/exclusion criteria will be re-confirmed at both study visits by the above procedures as well as a medical history and physical exam. Participants will be randomly assigned to drug order (prazosin 1st vs. 2nd visit) in a stratified blocked schedule by sex and group (alcoholic vs. control) using urn randomization procedures⁸⁵. The randomization and double-blind will be implemented and maintained by the UW Pharmaceutical Research Center, which is located in the same building in the UW hospital as all study visits in the CRU. All participants are told that they will receive both 2mg of prazosin and placebo, one agent at each study visit. Drug/placebo order is counterbalanced between participants. However, neither participants nor researchers will be aware of whether prazosin or placebo is administered at each visit.

All subsequent procedures will be identical at the first and second study visits except for the assessment of study eligibility and the drug administered. Alcoholic participants will complete a brief alcohol craving questionnaire, a 6 item subset of the 14-item version of the Desires for Alcohol Questionnaire (DAQ⁸⁶) to determine baseline craving levels. Women of childbearing potential participants will provide a urine sample to verify they are not pregnant. All participants will then provide a breath sample to verify an initial blood alcohol concentration (BAC) of 0.00 (Alcosensor IV; Intoximeters, Inc.). All participants will be asked to refrain from consuming alcoholic beverages or any other psychoactive drugs for 24 hours prior to the experimental session, to avoid any acute effects of alcohol. Next all participants will ingest one pill with a full glass of water.

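### The control criteria contradict each other on nicotine dependence, and no committed analysis adjusts the non-randomised Aim 2 group contrast for smoking

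*Combined protocol and SAP*

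**What the plan says.** **Control eligibility.** Under Inclusion Criteria, controls must not meet criteria for "any current or lifetime history or substance dependence other than nicotine dependence". Under Psychological/Behavioral exclusion, the control-only line reads "Control Participants Only: Lifetime history of substance dependence", with no exception. The line just above it, for everyone, does carry one: "Any current active substance use disorder other than tobacco". The Overview of Study Procedures describes the SCID module as confirming "no lifetime history of substance dependence for control participants", again without an exception.

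**Matching.** Participant Population and Recruitment says the groups will be "matched on selected characteristics including age, sex, education level, daily nicotine use, and Axis I psychopathology", and adds: "These characteristics will be matched at the group level such that the average and range of both groups will be comparable". No tolerance is given.

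**The 24-hour rule.** All participants are asked to "refrain from consuming alcoholic beverages or any other psychoactive drugs for 24 hours prior to the experimental session". Nicotine is neither named nor exempted. The only abstinence test described there is breath alcohol, and Table 1 lists no item for last nicotine use.

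**Why nicotine matters here.** Preliminary Evidence reports: "Cigarette smokers displayed elevated startle response selectively during unpredictable stressors (vs. predictable stressors) after 24-hours of nicotine deprivation", compared with non-deprived smokers.

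**Analysis.** Only drug order is randomised. The Statistical Analysis section commits to Group, Drug Order and days abstinent as between-subject terms, and tests Aim 2 as Group x Condition. Tobacco use is listed among measures that may be added in secondary analyses, as a possible moderator of drug effects.

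**The concern.** A nicotine-dependent volunteer without alcoholism is eligible under the inclusion criterion and ineligible under the exclusion list and the SCID check. If staff follow the latter two, smokers become scarce among controls while remaining admissible among alcoholics, and matching on daily nicotine use becomes hard to achieve.

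By the protocol's own account, nicotine deprivation produces the signature that Aim 2 looks for. If smokers deprived at the session are more common among alcoholics, part of a Group x Condition effect could be nicotine withdrawal read as alcohol-related stress reactivity. Matching is the only committed protection. The one place where tobacco use enters the analysis plan is optional and concerns drug effects, not confounding of the group contrast.

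**Working it through.** **1. The criteria side by side.**

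| Place | Nicotine-dependent control |
|---|---|
| Inclusion, controls | allowed |
| Exclusion, everyone (current disorder) | allowed |
| Exclusion, controls only (lifetime dependence) | barred as written |
| SCID check | barred as written |

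The four lines cannot all hold.

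**2. The plan's own power figure.** Inputs: N = 72, ΔR² = .10, R² = .30 (stated for the three-way Aim 3 effect). f² = .10/(1 − .30) = 0.143. With one numerator df, 64 residual df (72 minus 8 terms for Group x Order x days) and two-sided 5% (assumed; no alpha is stated), power is 85.6%, against the stated 85%. That figure is not in dispute.

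**3. Bias in the Aim 2 contrast.** Use one score per person, unpredictable minus predictable, averaged over visits, with residual SD 1. If deprivation adds δ, then

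bias = δ × (deprived share in alcoholics − deprived share in controls).

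The documents give neither δ nor any share. Assume δ = 0.3 to 0.75 SD, 36 per group and, first, that every smoker is deprived. Type I error below comes from simulating a planned model with Group, Order, Group x Order, days abstinent and days x Order (66 residual df). Days are centred in alcoholics and set to 0 in controls, since the plan gives controls no value. That coding makes Group x days redundant, which is why the df differ from the 64 in step 2.

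| Smokers, alcoholic vs control | Difference in share | Bias (SD) | Type I error |
|---|---|---|---|
| 11 vs 11 | 0 | 0 | 3.6–4.8% |
| 15 vs 11 | 4/36 = 0.111 | 0.03–0.08 | 4.9% |
| 18 vs 11 | 7/36 = 0.194 | 0.06–0.15 | 5.6–7.2% |
| 22 vs 11 | 11/36 = 0.306 | 0.09–0.23 | 6.4–12.9% |
| 11 vs 0 | 11/36 = 0.306 | 0.09–0.23 | 6.5–14.5% |

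The value below 5% at 11 vs 11 arises because an exactly balanced but unmodelled smoker effect inflates the residual variance.

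**4. Which covariate removes it.** Adding smoker status (yes/no) brings every all-deprived setting re-run (all rows above except 18 vs 11) back to about 5% (4.6–5.2%; 6,000 trials per setting, Monte Carlo error about 0.3 points). Smoker status is then exactly the simulated cause, so this is its best case. Daily amount alone (assumed gamma, mean 12.5 per day, 0 in non-smokers) at δ = 0.75 leaves 0.10 SD for 22 vs 11 and 0.08 SD for 11 vs 0, with type I error about 6%.

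**5. Unequal deprivation among smokers.** With smoker status in the model, the remaining bias is δ times the deprivation difference among smokers, weighted by stratum size.

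- 14 vs 14 smokers, 10 vs 4 deprived: weights 14×14/28 = 7 and 22×22/44 = 11. (10/14 − 4/14) × 7/18 = 0.167, so 0.05–0.13 SD, the same as without the term.
- 22 vs 11 smokers, 15 vs 3 deprived: weights 22×11/33 = 7.33 and 14×25/39 = 8.97. (15/22 − 3/11) × 7.33/16.31 = 0.184, so 0.06–0.14 SD, down from 12/36 × δ = 0.10–0.25 SD.

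Adding deprived-at-session (yes/no) removes the bias in both; type I error is about 5%.

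**6. Price of the smoker term.** SE inflation is 1/√(1 − r²), with r the Group–smoker correlation: 1.007 at 15 vs 11, 1.05 at 22 vs 11, 1.10 at 11 vs 0. Borrow the Aim 3 power inputs for Aim 2 (an assumption) and let smoker status explain nothing. One extra term (63 df) then moves power from 85.6% to 85.1% if balanced, 81.5% at 22 vs 11 and 77.5% at 11 vs 0.

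**7. Aims 1 and 3.** Drug x Condition and Drug x Group x Condition are within-person drug contrasts. A stable nicotine effect cancels from them, and an additive between-subject regressor with its Condition interaction leaves both estimates unchanged.

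**The case against.** The strongest reply is that the eligibility conflict is a drafting slip with recoverable intent. The inclusion criterion names the nicotine exception, matching on daily nicotine use presupposes nicotine users in both groups, and the neighbouring exclusion exempts tobacco. On that reading the 11 vs 0 case needs staff to apply the bare exclusion and then to miss the matching target. The 24-hour rule covers both groups alike, so its silence on nicotine creates no group bias by itself. Every imbalance in the tables is assumed, and where matching succeeds or nearly succeeds there is no material inflation.

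Much of this stands, and it is why the point is minor. It does not remove it. The exclusion list and the SCID check are what screening staff apply, and both omit the exception. Matching on average and range has no tolerance, and matching on daily use does not make smokers in the two groups arrive equally deprived.

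A reader might also infer that sex is an unaddressed confounder. The documents do not support that: sex is a matching variable, and no gain from adjusting for it has been shown. Nor do they show that smokers will be required to abstain from nicotine; the rule is silent.

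**Conclusion.** The contradiction in the control criteria is real on the text. The lack of a committed nicotine term leaves the Aim 2 contrast dependent on matching that the literal exclusion would undermine. The bias is zero if the groups match on smoking and their smokers abstain alike. On assumed inputs (0.3 to 0.75 SD, all smokers deprived) it is about 0.09 to 0.23 SD, with type I error about 6 to 15%, at a gap of 11 smokers in 36.

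A reader might go further and conclude that Aim 2 is confounded, or that the prazosin results are compromised. Neither follows. The documents contain no smoking data and no evidence of differential abstinence. Aim 1 is not confounded, and Aim 3 would be touched only if nicotine modified the drug effect and also differed by group. Minor priority.

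**What to change.** - Reconcile the control inclusion criterion, the control-only exclusion and the SCID description on nicotine dependence. Which rule applies is for the investigators.
- State in the Overview of Study Procedures whether nicotine falls under the 24-hour rule.
- For the Aim 2 startle and self-report contrasts only, prespecify current smoker status (yes/no) as an additive between-subject regressor with its Condition interaction. Daily amount, with its own Condition interaction, may be added as a further term but should not replace smoker status.
- Record last nicotine use at each visit, list it in Table 1, and prespecify an Aim 2 sensitivity analysis that adds nicotine-deprived at session (yes/no, non-smokers coded no).
- Do not add a sex term on these grounds.

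The cost is a few sentences, one recorded item per visit, one or two residual df in the main Aim 2 model (one more in the sensitivity analysis), and an Aim 2 standard error that grows with imbalance, by about 10% at 30% vs 0% smokers. Smoking status itself should need no new collection, since matching on daily nicotine use presupposes it.

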animals and humans. Christian Grillon at NIH has developed a cued-stressor task called the “No Shock, Predictable Shock, Unpredictable Shock” (NPU) task to carefully contrast response to unpredictable vs. predictable stressors^{50,51}. Predictable shock conditions involve administration of 100% cue-contingent, imminent electric shock. Unpredictable shock conditions involve temporally uncertain administration of shock. Startle potentiation during unpredictable shock (relative to no-shock blocks) provides the primary measure of negative affective response to stressors that in rodents engages both NE system activity and elicits etiologically relevant behaviors for addiction (i.e., stressor-induced reinstatement). This task represents a direct translation of methods and measures used by Davis, Walker and colleagues to parse neural mechanisms involved in response to unpredictable vs. predictable stressors^{35,43}. We will use this task in the proposed research with humans.

PRELIMINARY EVIDENCE

Research from our lab provides compelling evidence that unpredictable stressors elicit startle potentiation that is attenuated by anxiolytic drugs and exacerbated by abstinence in drug dependent users. Alcohol administration robustly suppresses startle potentiation during tasks involving unpredictable stressors, including the NPU task^{52,53}. Similarly, benzodiazepines reduce startle potentiation to unpredictable stressors⁵⁴. Furthermore, these anxiolytic effects are specific to unpredictable stressors as these drugs produce minimal effects on startle potentiation to predictable stressors. These studies provide evidence that startle potentiation in the NPU and similar tasks is a sensitive index of the effects of pharmacologic agents on negative affective response to stressors.

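### Benzodiazepine use without a use disorder is not excluded, although the protocol says this class selectively lowers the response on which all three aims are tested

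*Combined protocol and SAP*

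**What the plan says.** The Exclusion Criteria section marks with an asterisk those exclusions made for scientific rather than safety reasons. Under Medications/Therapies exclusion, the asterisked items are stimulants and "Beta-blockers (e.g., propranolol), alpha2 agonists (e.g., clonidine, guanfacine), and SNRI anti-depressants (e.g., venlafaxine, duloxetine"). The reason given is the same for both: "Excluded because these medications directly alter CNS noradrenergic neurotransmission". No item names benzodiazepines or other anxiolytics.

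In Background and Significance, under Preliminary Evidence, the protocol says that "benzodiazepines reduce startle potentiation to unpredictable stressors" and that "these anxiolytic effects are specific to unpredictable stressors as these drugs produce minimal effects on startle potentiation to predictable stressors". The section on the NPU task states: "Startle potentiation during unpredictable shock (relative to no-shock blocks) provides the primary measure of negative affective response to stressors". The Statistical Analysis section judges Aim 1 on Drug x Condition, Aim 2 on Group x Condition and Aim 3 on Drug x Group x Condition, where Condition is unpredictable versus predictable shock.

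Four other provisions bear on the point:

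- The Psychological/Behavioral exclusions remove anyone with a current substance use disorder other than tobacco, and controls with a lifetime history of substance dependence.
- Overview of Study Procedures says: "All participants will be asked to refrain from consuming alcoholic beverages or any other psychoactive drugs for 24 hours prior to the experimental session". The purpose given there is to avoid acute effects of alcohol. The only objective check described is breath alcohol.
- Table 1 records concomitant medications, marked at Visit 1.
- Medication use is neither a group-matching variable (Participant Population and Recruitment) nor among the moderators listed as examples in Statistical Analysis.

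**The concern.** The protocol excludes drugs that act on the mechanism under study, but not a class that it says acts on the outcome. By the protocol's account the benzodiazepine effect is confined largely to the unpredictable condition. It therefore does not cancel in the unpredictable-minus-predictable contrast; it shifts that contrast directly.

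The crossover does not protect Aim 2, which compares groups. Alcoholic participants are sought in part through "local in- and out-patient treatment facilities for alcoholism", so unequal use between groups is plausible, though not documented. In Aims 1 and 3 each person is compared with himself or herself. Stable use would not bias that comparison, but it would leave less unpredictable potentiation for prazosin to reduce, and so dilute the effect.

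The 24-hour request leaves the user's state at testing undefined. If prescriptions are outside it, users are tested under a drug that lowers the outcome. If they are inside it, regular users are tested after withholding the drug, and the protocol reports that deprivation from other drugs raises this response.

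**Working it through.** **1. Who is left in the gap.** The scientific exclusions do not reach benzodiazepines. The use disorder exclusion removes disordered use. The 24-hour request is not an eligibility rule, is not verified for anything but alcohol, and is silent on prescriptions. What remains is prescribed or occasional use without a disorder, with drug state at testing unknown.

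**2. Aim 2, illustrative size.** The documents give 36 participants per group, but no rate of use, no suppression and no group difference. All of the following are assumptions:

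- share of alcoholics using a benzodiazepine, p = 10-30% (about 4 to 11 of 36);
- reduction of unpredictable potentiation in users, s = 20-40%;
- no users among controls, and the 24-hour request without effect;
- control mean 1.00, alcoholic mean 1 + d with d = 0.20, predictable potentiation equal in both groups and unaffected.

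The alcoholic mean falls by the fraction p x s. The share of the group difference lost is p x s x (1 + d) / d.

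- Low: 0.10 x 0.20 = 2%; 0.02 x 1.20 = 0.024; 0.024 / 0.20 = 12%.
- Middle: 0.20 x 0.40 = 8%; 0.08 x 1.20 = 0.096; 0.096 / 0.20 = 48%.
- High: 0.30 x 0.40 = 12%; 0.12 x 1.20 = 0.144; 0.144 / 0.20 = 72%.

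The answer depends strongly on d. With d = 0.10 the range is 0.02 x 1.10 / 0.10 = 22% to 0.12 x 1.10 / 0.10 = 132% (a reversed sign). With d = 0.50 it is 0.02 x 1.50 / 0.50 = 6% to 0.12 x 1.50 / 0.50 = 36%.

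It also depends on imbalance. If controls used at the same rate with the same suppression, both means would shrink by p x s and the difference would lose only 2% to 12%.

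**3. The plan's own power figure.** Power Analyses for Sample Size Justification gives 85% at N = 72 for the Aim 3 effect, with an R-squared increment of .10 in a model with R-squared .30. So f2 = .10 / (1 - .30) = 0.143. With a 1-df F test, alpha .05 (assumed), k predictors (not stated), v = 72 - k - 1 and noncentrality f2 x (v + 2), power is 85.6% for k = 7 and 85.1% for k = 8. The stated figure reproduces.

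**4. Aim 3, illustrative dilution.** Suppose that the mean prazosin effect among alcoholics falls by L = p x s, in proportion to the suppressed potentiation. Let r be the ratio of the control effect to the alcoholic effect. The interaction is then multiplied by ((1 - L) - r) / (1 - r), and the R-squared increment by the square of that. With k = 7 and residual variance unchanged:

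| L | Power, r = 0 | Power, r = 0.5 |
|---|---|---|
| 0 | 86% | 86% |
| 2% | 84% | 83% |
| 8% | 79.5% | 72% |
| 12% | 76% | 63% |

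Example: L = 8%, r = 0.5 gives (0.92 - 0.5) / 0.5 = 0.84; .10 x 0.84 squared = .0706; power 72%.

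**5. The opposite direction.** The deprivation findings in Preliminary Evidence concern tobacco, marijuana and alcohol. If they carried over to withheld benzodiazepines, unequal use would inflate the Aim 2 difference. The documents give nothing from which to size this.

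**The case against.** A list built on mechanism is a coherent choice for a study of an alpha1 antagonist, and each added drug class costs recruitment and generality. The use disorder exclusion already removes the heaviest users. Matching on Axis I psychopathology would partly balance prescribing for anxiety, and mood/anxiety comorbidity is an available moderator. Recruitment also runs through community flyers and online advertisements, and nothing says that the treatment facilities prescribe benzodiazepines to people one to eight weeks abstinent. The eligibility list and the 24-hour request are also different kinds of rule, so they do not strictly contradict each other.

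Much of this stands as a limit on size. It does not close the gap: use without a disorder passes every stated criterion, and neither matching nor the listed moderators include medication.

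A reader might infer three stronger things that the documents do not support:

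- That users sit at a floor, leaving prazosin nothing to reduce. The protocol says only that potentiation is lowered. Under complete suppression, 10-30% users would cut Aim 3 power to 78-56% (r = 0) or 68-23% (r = 0.5), but that is an outer bound.
- That the effect must mask Aim 2. The direction depends on whether users are tested on the drug or after withholding it, and extending the deprivation findings to non-disordered benzodiazepine users is itself an extrapolation.
- That about half of the Aim 2 effect is lost. The 48% is one point in a range that rests wholly on assumed inputs.

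**Conclusion.** The point holds in a limited form. By the protocol's own account, benzodiazepines act selectively on the contrast that decides all three aims, and prescribed or occasional use without a disorder is neither excluded nor planned for in the analysis. Aim 2 could be biased in either direction if use differs between groups; Aims 1 and 3 could be diluted by suppressed users.

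The size is unknown. Under the stated assumptions, the loss of the Aim 2 difference runs from about 12% to 72%, and Aim 3 power falls from 86% to between 84% and 63%. All of these presume no control users and no effect of the 24-hour request. With no users enrolled, the loss is zero and the planned 85% stands. The case for acting rests on the protocol's statement about the outcome and on the low cost of the remedy, not on any one of these figures.

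**What to change.** 1. Add current benzodiazepine use to the asterisked scientific exclusions under Medications/Therapies exclusion, citing the Preliminary Evidence section as the reason. Word it as an enrolment criterion only, not as a request that anyone stop a prescribed drug.
2. For anyone enrolled while using, report benzodiazepine use by group from the concomitant-medication record in Table 1, and prespecify a sensitivity analysis of Aims 2 and 3 without users. Because Table 1 marks that record at Visit 1 only, state how use at Visit 2 will be known. Show the matching variables again in the reduced set, since dropping users may disturb the group matching.
3. Reconcile the medication exclusions with the 24-hour request in Overview of Study Procedures: say whether the request applies to prescribed medication. Which rule is clinically right is for the investigators.

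The cost is one criterion line, one clarifying sentence, one extra analysis on data mostly collected already, and a slightly smaller pool of eligible participants.
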